### **4.3 Discontinuation from study treatment**

Patients may be discontinued from AZD9291 treatment in the following situations:

- The investigator thinks that it is in the patient's best interest to stop therapy (i.e. disease progression or patient is no longer receiving clinical benefit)
- Patient decision: the patient is at any time free to discontinue treatment, without prejudice to further treatment.
- Confirmed diagnosis of ILD
- Ulcerative ocular events
- QTc interval prolongation with signs/symptoms of serious arrhythmia
- Other manifestation of unacceptable toxicity
- Pregnancy
- Patient incorrectly enrolled or treated on the study
- Patient starts receiving additional anti-cancer therapy

- Lost to follow up (unsuccessful contact with patient despite every effort made by investigator)
- Termination of the study (see Sections 4.4 and 10.2.4)

All unused investigational product (IP) must be returned by the patient or representative (e.g. caregiver, family member).

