### **Duration of IP administration**

Patients may continue to receive AZD9291 as long as they continue to show clinical benefit, as judged by the investigator, and in the absence of discontinuation criteria (see section 4.3).

Enrolment will be closed within 6 months of market license approval in that country or at national reimbursement, whichever is sooner.

The study will be closed in each participating country as soon as possible following national reimbursement of AZD9291 in that country (up to a max of 90 days post reimbursement).

Patients withdrawing from the treatment prior to national reimbursement will be followed up as part of this study until death or lost to follow-up.

At national reimbursement patients still on treatment will be transitioned to commercial supply as long as the patient is benefitting from treatment as per investigator assessment, and in accordance with national regulations in the countries where the study is conducted.

In the event that national reimbursement should not be granted following a reasonable time after market license approval in the country, the study will be closed in a maximum period of 18 months after the last patient is enrolled in that country. Contingencies will be made locally to ensure continued drug supply for patients who are still deriving benefit from AZD9291 at that time.

If applicable, timelines for conversion to commercial drug will be agreed with local bodies which may include regulatory agencies, ethics committees, and institutions.

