#### **4.3.1 Procedures for discontinuation of a subject from study treatment**

Any subject who discontinues study treatment for reasons other than disease progression should have tumour assessments performed as scheduled in the protocol (see Table 4) until disease progression is documented or death occurs, unless consent is withdrawn.

Patients may continue study treatment beyond disease progression if they are still receiving clinical benefit, as judged by the Investigator, and in the absence of any other discontinuation criteria.

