### **6.6.2 QTc Prolongation (using Fredericia’s formula –QTcF–)**

Patients with Grade 3 QTcF with QTcF prolongation (i.e., confirmed QTcF prolongation to > 500 ms absolute or a > 60 ms increase from baseline) should have AZD9291 interrupted and regular ECGs performed until resolution to baseline. If the QTcF interval resolves to Grade 1 (<481 msec), AZD9291 may be restarted at the reduced dose of 40 mg. If the QT prolongation does not resolve to  $\leq$ CTCAE grade 1 (<481 msec) after 3 weeks, then the patient will be permanently withdrawn from AZD9291 and observed until resolution of the toxicity.

All QTcF prolongation of >470 ms at any point during the study must be reported to AstraZeneca, and ECGs sent to the Study Team upon request for further analysis. This does not alter the management guidance outlined above.

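### The protocol does not reconcile its stopping criterion for QTc prolongation with serious arrhythmia with its rule for restarting after QTcF prolongation

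*Protocol*

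**What the plan says.** Four places in the protocol bear on a patient whose QTc prolongation comes with signs or symptoms of serious arrhythmia.

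- **Synopsis, Duration of IP administration.** Patients may stay on drug while they benefit in the investigator's judgement and "in the absence of discontinuation criteria (see section 4.3"). Section 4.3.1 uses similar language for treatment beyond progression: "in the absence of any other discontinuation criteria".
- **Section 4.3.** The list includes "QTc interval prolongation with signs/symptoms of serious arrhythmia". Its lead-in is permissive: "Patients may be discontinued from AZD9291 treatment in the following situations".
- **Section 6.6.2.** Patients with Grade 3 QTcF prolongation, spelled out as a confirmed value above 500 ms or a rise of more than 60 ms from baseline, "should have AZD9291 interrupted and regular ECGs performed until resolution to baseline". Then: "If the QTcF interval resolves to Grade 1 (<481 msec), AZD9291 may be restarted at the reduced dose of 40 mg". Permanent withdrawal is required only if QTcF has not come back to Grade 1 or lower after 3 weeks. Arrhythmia is not mentioned.
- **Section 6.6, general rule.** For toxicity of grade 3 or higher, or unacceptable toxicity of any grade, dosing is interrupted. It may restart at 80 mg or 40 mg if the event improves to grade 2 or lower within 3 weeks. The decision rests on the investigator's evaluation and/or discussion and agreement with the Medical Monitor as needed. Arrhythmia is not mentioned here either.

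**The concern.** QTc prolongation is one of the two adverse events of special interest that the protocol names, and section 3.2 excludes patients with factors that raise the risk of QTc prolongation or arrhythmic events. A patient who develops prolongation with signs of serious arrhythmia on treatment is the case in which a site most needs a clear instruction. Section 4.3 makes the event a ground for stopping. The section a site would open to manage the event, 6.6.2, describes a route back to treatment and does not separate patients with arrhythmia from those with an ECG finding alone.

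What is at stake is patient safety and uniform conduct across sites. One site could stop permanently on the strength of the synopsis and 4.3. Another could re-dose at 40 mg on the strength of 6.6.2. Each would be following the protocol as written.

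**Working it through.** No arithmetic applies, and the plan states no figure on this point. The check is to take one patient through each provision.

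**The patient.** Confirmed QTcF above 500 ms with signs of serious arrhythmia. Dosing is interrupted, and QTcF falls below 481 ms within 3 weeks.

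| Provision | Answer for this patient |
|---|---|
| Synopsis, read with 4.3 | A listed criterion is present, so dosing does not continue |
| 4.3 on its own | Discontinuation is permitted |
| 6.6.2 | Restart at 40 mg is permitted; the 3-week withdrawal rule is not triggered |
| 6.6, if the event is graded above 3 | Restart is permitted on improvement to grade 2 or lower within 3 weeks, subject to investigator and/or Medical Monitor judgement |

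**Step 1: do 4.3 and 6.6.2 contradict each other?** Taken alone, no. One says the drug may be stopped and the other says it may be restarted, and both can be true.

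**Step 2: does the synopsis settle it?** There are two readings.

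- If meeting a 4.3 criterion bars further drug permanently, the synopsis forbids what 6.6.2 permits.
- If it does not, the synopsis leaves restart open, and 6.6.2 then lets this patient restart on QTcF alone. The second reading has some support: "Other manifestation of unacceptable toxicity" is also a 4.3 item, yet 6.6 allows restart after unacceptable toxicity. That item is a residual one that depends on judgement, so it is weak evidence about a specifically named event.

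The text does not say which reading applies. Under neither reading does it give an express instruction on restart for a patient who had arrhythmia.

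**Step 3: does another section supply the missing instruction?** For other 4.3 events the protocol does this. Section 6.6.1 requires permanent discontinuation for confirmed ILD, 6.6.3 forbids restart after corneal ulceration, and 6.5.1 requires immediate discontinuation in pregnancy. Section 6.6.2 has no equivalent sentence for arrhythmia.

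**Step 4: do the safeguards answer the question?** Section 6.6.2 requires repeated ECGs and says that any QTcF above 470 ms "at any point during the study must be reported to AstraZeneca", but adds that this reporting leaves the management guidance unchanged. An arrhythmia that meets the SAE criteria is reported within 24 hours under 6.3. These measures monitor and report the event. They do not say whether the patient may restart.

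**The case against.** The strongest reply is that the provisions fit together. Section 6.6.2 handles an ECG finding defined in milliseconds, while 4.3 adds a clinical condition, arrhythmia, as a further ground for stopping. On that view, a site that sees both would stop, and the synopsis supports it. Nothing in 6.6.2 compels re-dosing. Section 6.6 refers restart to the investigator and/or the Medical Monitor, and section 4.1 requires confirmation of continuing benefit at each re-supply. Much of this stands. A reader might infer that sites are given three opposing commands, or that 6.6.2 requires re-dosing. The documents do not support either inference, because 4.3 and 6.6.2 both use permissive language and leave room for clinical judgement.

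A second reply is that 6.6.2 opens with Grade 3, and prolongation with serious arrhythmia may be graded higher. The documents do not reproduce the CTCAE grades for QTc, so this cannot be ruled out. It does not close the gap. An event above Grade 3 falls under the general rule in 6.6, which covers grade 3 or higher and also allows restart.

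A third reply is that the sponsor may never have meant to bar re-challenge. The version 2.0 history says the item was added to 4.3 as a discontinuation criterion to align with the sponsor's project safety requirements. Those requirements are not in the documents. A reader might infer from the entry that a permanent stop was intended, but it does not say so.

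What survives is that the natural reading has to be supplied by the site. A site that follows 6.6.2 as written, or 6.6 for a higher-grade event, may re-dose a patient for whom the synopsis and 4.3 together indicate a stop.

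**Conclusion.** The point holds as an inconsistency in a safety rule that should be corrected. For one event type the current text supports both no further drug and 40 mg daily, and no provision says which prevails. The conclusion rests on the current protocol wording and on taking the synopsis reference to 4.3 as carrying some force. It does not depend on how the event is graded, since 6.6.2 and 6.6 both allow restart.

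The documents give no incidence for this event, so no patient count is offered. A reader might infer that the ambiguity affects the study's estimates. The documents give no basis for that, and no effect on overall survival or any other analysis is claimed.

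**What to change.** Make three small text changes.

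1. Add to 6.6.2: *Patients with QTc prolongation and signs/symptoms of serious arrhythmia must permanently discontinue AZD9291 and must not restart; the 40 mg restart applies only to QTcF prolongation without such signs/symptoms.*
2. Add the cross-reference *(see 6.6.2)* to the QTc item in 4.3. Leave the 4.3 lead-in as it is. The list also covers disease progression, and 4.3.1 allows treatment beyond progression, so making the whole list mandatory would create a new conflict.
3. Add *except as stated in 6.6.1 to 6.6.3* to the restart rule in 6.6, which closes the same gap for events graded above 3.

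The changes can go to sites as a safety clarification and into the next amendment. Data collection and analysis are unchanged. The downside is that an investigator loses the discretion to re-challenge these few patients at 40 mg, which is a reasonable price for a clear rule on a serious arrhythmic event.

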## **2. STUDY OBJECTIVE**

The primary objective of this study is to assess the efficacy and safety of single agent AZD9291 in a real world setting in adult patients with advanced or metastatic, epidermal growth factor receptor (EGFR) T790M mutation-positive Non-Small Cell Lung Cancer (NSCLC), who have received prior EGFR-tyrosine kinase inhibitor (TKI) therapy.

The primary efficacy outcome is OS, with secondary efficacy outcomes including investigator assessed response rate, investigator assessed PFS and Time to Treatment Discontinuation (TTD).

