### 6.6.1 Pulmonary Symptoms

If new or worsening pulmonary symptoms (e.g., dyspnea) or radiological abnormality suggestive of interstitial lung disease are observed, the administration of AZD9291 needs to be interrupted and the study Medical Monitor must be informed. It is strongly recommended to perform a full diagnostic workup, to exclude alternative causes such as lymphangitic carcinomatosis, infection, allergy, cardiogenic edema, or pulmonary hemorrhage. The results of the full diagnostic workup (including high-resolution computed tomography, blood and sputum culture, haematological parameters) will be recorded in the CRF by the investigator. Where ILD is suspected, local practice must be followed in discussion with the study Medical

Monitor. In the absence of a confirmed diagnosis of ILD, AZD9291 may be restarted following consultation with the study Medical Monitor. In case of a confirmed diagnosis of ILD, AZD9291 must be permanently discontinued. (refer to “Guidance for the Management of AE in studies using 80mg AZD9291”)

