### 2.2 Violations and deviations

All major deviations related to the study inclusion or exclusion criteria and study conduct will be listed and summarised.

The following general categories will be considered major deviations. This list is not exhaustive and additional important deviations may be added prior to database lock.

- Informed consent procedure deviation Missing subject' signature from the informed consent document or other International Conference on Harmonisation - Good Clinical Practice (ICH-GCP) violation related to informed consent; laboratory or urinalysis samples or electrocardiogram (ECG) date before informed consent date and not performed per standard of care but on study purpose)
- Eligibility criteria deviation (any inclusion criteria not met or exclusion criteria met)
- Prohibited medication deviation (e.g., patients received other anticancer agents, investigational agents, or radiotherapy while on study treatment)
- Procedures/Tests deviation (ECG or ophthalmologic assessment or WHO performance status not performed at screening visit)
- Investigational product administration deviation (Overdose; Screening assessment date not within 28 days before start of treatment; Incorrect procedure for T790M obtainment; New or worsening pulmonary symptoms or radiological abnormality suggestive of Interstitial Lung Disease (ILD) observed, but study treatment not interrupted; Patient experiencing grade 3 QT interval corrected per Fredericia's formula (QTcF) with QTcF prolongation, but study treatment not interrupted)
- Withdrawal criteria deviation (Any withdrawal criteria met)
- Adverse Event (AE) / Serious Adverse Event (SAE) deviation (SAE / AE of special interest not reported in CRF within 24 hours of become aware)

The categorization of these as major deviations is not automatic and will depend on the duration and the perceived effect on efficacy.

All protocol deviations are defined in Protocol Deviation Specification document version 5.0 where a category Programmable / Observable is assigned to each deviation. Programmable deviations are programmed while Observable are checked manually during monitoring visits. Programmable deviations are then imported, and observable deviations are entered in a Protocol Deviation Tool according to classification defined in the Protocol Deviation

Specification. All deviations are then reviewed and classified on a monthly basis as Major/Minor.

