### 3.1.4 Response Rate (RR)

Response Rate is defined as the number (%) of patients with a best response (according to investigator assessment as recorded in the tumour evaluation CRF) of ‘responding’, regardless of the method of evaluation, and will be based on a subset of the FAS consisting of patients with at least one documented response assessment. Data obtained up until progression, or last evaluable assessment in the absence of progression, will be included in the assessment of response rate. Patients who discontinue treatment without progression, receive a subsequent anti-cancer therapy and then respond will not be included as responders in the RR.

In addition, a sensitivity analysis of RR will be performed including patients who died prior to any response assessment and classifying them as non-responders.

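### The response-rate rule in SAP 3.1.4 counts a pre-progression response first recorded after other anti-cancer therapy was added to ongoing AZD9291

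*Protocol*

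**What the plan says.** **Objective.** Protocol Section 2 aims to "assess the efficacy and safety of single agent AZD9291 in a real world setting". RR by investigator assessment is a secondary efficacy outcome.

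**Response rule.** SAP 3.1.4 takes the best investigator-recorded response, by any method of evaluation, using data up to progression or, without progression, up to the last evaluable assessment. It has one rule on other therapy: "Patients who discontinue treatment without progression, receive a subsequent anti-cancer therapy and then respond will not be included as responders in the RR".

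**Overlap is foreseen.** SAP 2.2 gives this example of a prohibited-medication deviation: "patients received other anticancer agents, investigational agents, or radiotherapy while on study treatment". Classification as major is not automatic. Deviating patients stay in the full analysis set, and a sensitivity analysis prompted by deviations is optional.

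**Stopping AZD9291.** Protocol 4.3 opens with "Patients may be discontinued from AZD9291 treatment in the following situations" and includes in its list "Patient starts receiving additional anti-cancer therapy". The synopsis (Duration of IP administration) makes continued treatment conditional: "in the absence of discontinuation criteria (see section 4.3". Section 4.3.1 sets a like condition for treatment beyond progression: "in the absence of any other discontinuation criteria".

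**The concern.** By withholding responses that follow a switch to another therapy, SAP 3.1.4 accepts that such responses should not be credited to AZD9291. The rule is triggered only if AZD9291 stops first. When the other therapy is added on top of AZD9291, the cause of a later response is also uncertain, yet the response is credited to AZD9291 in full.

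At stake is what RR means in a study described as single agent. Counting these cases can only move RR upwards. RR is also tabulated in many subgroups (SAP 4.2.7), where a few such patients weigh more. Overall survival, the primary efficacy outcome, is not affected.

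**Working it through.** **1. Apply the rule to each order of events.** This is a question of logic, so the cases are set side by side. In all of them the patient has no response recorded before the last event named, except in case E.

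| Case | Order of events | Result under SAP 3.1.4 |
|---|---|---|
| A | Progression, other therapy added, AZD9291 continues, response | Not counted: after the progression cut-off |
| B | AZD9291 stopped without progression, other therapy, response | Not counted: the exclusion applies |
| C | Other therapy added before progression, AZD9291 continues, response | Counted: neither rule applies |
| D | Other therapy starts before progression, AZD9291 then stopped because of it, response | Unclear: the therapy came before the stop, so it is not literally subsequent to it |
| E | Response, then other therapy | Counted, and no reason to change it |

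The gap is case C. Case D matters because the item in Protocol 4.3 is the start of the other therapy, so therapy comes first and stopping second.

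**2. Look for anything else that closes case C.**
- The planned RR sensitivity analysis (SAP 3.1.4 and 4.2.7) concerns only patients who died before any assessment.
- The deviation route in SAP 2.2 lists and summarises major deviations, but does not change RR.
- A deliberate policy of ignoring other therapy cannot be read into RR. SAP 3.1.2 states that policy explicitly for PFS, whereas SAP 3.1.4 contains an exclusion.

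**3. Size.** The plan gives no design figure for RR. Its only precision figures are for median OS. With 1,983 deaths and a median of 25 months, 25 × exp(±1.96/√1983) = 23.92 to 26.12 months, which matches the stated 23.9 to 26.1. That figure has no bearing on RR.

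The documents give no rate of added therapy, so the following is illustration only. Let *a* be the share of assessed patients who add other therapy before progression and before any response while on AZD9291, and *r* the share of those who then first respond. The share of all assessed patients affected is *f* = *a* × *r*, and not counting them lowers RR by *f*.

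- Assumed low: 0.01 × 0.10 = 0.001, or 0.1 point. With 3,500 patients (Protocol 9.5, an upper limit for the RR denominator), 3.5 patients.
- Assumed high: 0.05 × 0.30 = 0.015, or 1.5 points; 52.5 patients of 3,500.
- From an assumed RR of 60%, the middle of the 50% to 70% given in Protocol 1.4.2 for T790M-positive patients, RR becomes 60 − 0.1 = 59.9% or 60 − 1.5 = 58.5%.

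For scale, the exact (Clopper-Pearson) 95% half-width at RR 60% is 1.6 points for n = 3,500, 3.1 for n = 1,000 and 4.4 for n = 500. These are calculated here and are not stated in the plan.

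**4. Does the protocol let AZD9291 continue?** Section 4.3 is worded permissively. The synopsis and 4.3.1 make continuation depend on no criterion being met. Section 4.1 leaves anti-cancer treatment out of its general permission for concomitant treatment, then says nothing is restricted beyond the exclusion criteria, none of which names concurrent anti-cancer therapy. SAP 2.2 calls the overlap prohibited. These sections do not agree.

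**The case against.** **AZD9291 is not meant to continue.** A reader might infer from the permissive verb in 4.3 that a patient may simply stay on AZD9291 with another agent. The documents do not support that. The same list includes confirmed ILD, for which 6.6.1 says "AZD9291 must be permanently discontinued", and pregnancy, for which 6.5.1 also makes stopping mandatory. The verb therefore does not establish permission, and the synopsis, 4.3.1 and SAP 2.2 point the other way. This stands: the documents are inconsistent, not plainly permissive. It does not close the gap, because SAP 2.2 expects overlap to occur and SAP 3.1.4 does not say how to count it.

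**Most such responses are already excluded.** A reader might infer that only responses after AZD9291 has stopped are removed. That overlooks the progression cut-off in the same paragraph, which removes case A. This stands and confines the point to therapy added before progression.

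**The asymmetry is defensible.** While AZD9291 continues, it may itself have caused the response; after it has stopped, that is harder to argue. This has force. The proposed rule will drop some genuine AZD9291 responses, so *f* is an upper limit on the responses wrongly credited. It argues for showing RR both ways, not for leaving the case unaddressed.

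**The effect is small and unproven.** RR is secondary, no tests are performed, and every input to the size is assumed. This stands. Two stronger inferences also fail. The bias cannot be said to rival the plan's stated precision for RR, because the plan states none. Nor do the documents show that the bias is largest in patients with brain metastases: they do not say that on-study radiotherapy is common there, and the SAP split is by prior radiotherapy.

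**Conclusion.** The point holds in a narrow form. SAP 3.1.4 has no rule for a response first recorded before progression after other anti-cancer therapy was added to ongoing AZD9291, so that response counts as a single-agent response. This follows from the text and needs no numerical assumption.

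The direction is certain: counting these cases can only raise RR. The size is not known. The range of 0.1 to 1.5 points rests wholly on the assumed 1% to 5% who add therapy and 10% to 30% of those who then respond, and the true figure may be negligible. The gap should be closed because the remedy is cheap and completes a rule the SAP already has. The inconsistency over continuing AZD9291 is a separate matter for the sponsor to reconcile; no view is taken here on which treatment rule is right.

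**What to change.** **SAP 3.1.4.** State that a response first recorded after the start of any anti-cancer therapy other than AZD9291, whether or not AZD9291 has been discontinued, is not counted as a response. Keep these patients in the denominator as non-responders. This settles cases C and D and leaves E unchanged. Say whether radiotherapy is included; SAP 2.2 already groups it with other anticancer agents. A rule limited to irradiated lesions is not shown to be feasible, because the tumour evaluation form described in SAP 3.1 records date, method and overall opinion, not lesions.

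**Identification and reporting.** Find the patients from the SAP 2.2 prohibited-medication deviations, major or minor, and the recorded therapy start dates. Report how many are affected, and RR both with and without them. State how partial dates are handled: SAP 4.1.1 moves a concomitant medication start with a missing day to the first of the month, which could place therapy before a response that in fact preceded it.

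**Cost.** One derivation rule and a few extra table lines. RR may fall slightly, and some genuine AZD9291 responses may be dropped, which the two-way display makes visible. Ascertainment is limited: Protocol Section 5 ties relevant concomitant medication to safety events, and although Table 4 has a general concomitant-medication row at treatment visits, it has none for other anti-cancer therapy or on-study radiotherapy. The count should be reported with that caveat.

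**Separately.** Reconcile the synopsis (Duration of IP administration), Protocol 4.1, 4.3 and 4.3.1, and SAP 2.2 on whether AZD9291 may continue once additional anti-cancer therapy starts.
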